## 3.6.4 Replacement of Subjects Lost to Follow-up and Withdrawal

An enrolled subject will be considered lost to follow-up or withdrawn as described in Section 3.6.3 at any point prior to Visit 6 (post-intervention follow-up visit). Subjects will not be replaced in this study.

#### 3.7 **Subject Completion**

An enrolled subject will be considered a study completer once any of the following three criterion is met:

- 1. Finishes all study visits without experiencing a urogenital CT or GC infection
- 2. Experiences urogenital CT infection
- 3. Experiences urogenital GC infection

#### 3.8 **Termination of the Study**

The study may be terminated at the discretion of the Sponsor. The study may also be terminated at a study site after discussion with the Sponsor. The reason for termination will be documented.

# 4 Study Products

## 4.1 Study Products Description

There are two study products used over the course of the intervention period for this study: 1) AMPHORA and 2) placebo.

#### **AMPHORA**

AMPHORA is in development as a vaginally administered contraceptive gel and microbicidal agent. AMPHORA is an acid-buffering gel (pH 3.5) containing three active ingredients (L-lactic acid 1.8%, citric acid 1%, and potassium bitartrate 0.4%) and the following non-active ingredients: benzoic acid, alginic acid, xanthan gum, glycerin, and water.

## Placebo (Universal Placebo Gel)

The placebo used in this study is universal placebo gel (UPG). UPG is an isotonic non-buffering gel, with pH adjusted to 4.5 and containing 2.7% hydroxyethylcellulose, sorbic acid, sodium hydroxide, sodium chloride, and purified water. In clinical studies, UPG has been proven safe and acceptable when used up to twice daily for 14 days (27).

**Table 2** Study Product Dosing

| Intervention Group | AMPHORA   | Placebo   |  |  |
|--------------------|---|---|--|--|
| Group A            | 422 subjects, 5 g dose applied up to 1 hour prior to coitus | N/A   |  |  |
| Group B            | N/A   | 422 subjects, 5 g dose applied up to 1 hour prior to coitus |  |  |

#### 4.1.1 Formulation and Packaging

For this study, pre-filled, single-use applicators will be used. The AMPHORA and placebo gels will be filled (5 g) into identical single-dose applicators consisting of an injection molded opaque white high-density polyethylene (HDPE) barrel with a rounded distal end for easy insertion. A thermoplastic rubber piston will be inserted at the opposite end of the barrel. This component will seal the end of the barrel to keep the contents stable over time and also functions as the applicator piston when in use. A HDPE plunger rod will be packaged alongside of the barrel within an aluminum overwrap. Product will be dispensed as a box of 10 overwrapped applicators with used applicator return bags and instructions for use.

#### 4.1.2 Product Supply

AMPHORA and placebo will be supplied by the Sponsor, Evofem, Inc., [name].

#### 4.1.3 Product Storage, Stability, and Expiration

The investigational product should be stored at room temperature (15°C-30°C). The investigational product will be maintained and dispensed by site research staff.

#### 4.1.4 Preparation

The investigational product is supplied ready for use. No preparation is necessary.

#### 4.1.5 Distribution to Subjects/Return of Unused Product and Used Applicators

Following screening, enrollment, and randomization, subjects will be issued a 4-week supply of investigational product based on the individual subject's projected usage. Each investigational product box contains 10 applicators. A subject could receive up to three boxes at a study visit during the intervention period. Subjects will be asked how many prefilled applicators they need, based on their number of sexual encounters per 4 weeks. At Visits 2 to 4 each, during the intervention period, subjects will return all unused product and used applicators packaged individually in plastic return bags provided and will be issued a new 4-week supply of investigational product based on projected usage. Unopened kits may be redispensed to the same subject, as appropriate. Subjects may be issued additional investigational product, as needed, should their supply be exhausted prior to the next study visit; however, excessive product usage should be brought to the attention of the Investigator and Sponsor. At Visit 5, subjects will return all unused product and used applicators.

#### 4.1.6 Administration

AMPHORA and placebo will be intravaginally administered by the subject in exactly the same manner. To administer, the plunger rod is inserted into the piston end of the barrel engaging the piston. The cap is removed from the distal end of the barrel; the barrel is then inserted into the subject's vagina (distal end first). The plunger rod is pushed into the barrel, subsequently moving the piston and gel toward the open end of the barrel. Only the gel will leave the barrel.

Detailed instructions for administration are included as **Appendix** C and supplied to the subject with the investigational product. Subjects will be trained in investigational product application prior to issuance.

## 4.1.7 Product Accountability

The Investigator will keep a record of the dates and amounts of investigational product received, the amount dispensed to study subjects, the amount returned from subjects at each visit (unused and used applicators) and the amount in inventory (not issued). These records should include the dates, quantities, and batch/serial numbers or kit numbers.

The Investigator will record drug accountability on a Drug Disposition Log, which will be monitored and confirmed by the Clinical Research Associate (CRA). Upon completion of the study and final drug accountability monitoring visit, all unused study medication will be returned to Evofem, Inc., or, if instructed by Evofem, Inc., unused investigational product may be destroyed onsite according to the site's standard operating procedures (SOPs).

## 5 Study Procedures/Evaluations

Subjects will undergo the following study procedures as indicated in this section and according to the Schedule of Assessments (Table 1). All equipment used should be calibrated and undergo routine calibration, as appropriate.

#### 5.1 Written Informed Consent

A written informed consent will be obtained from all study participants before start of any study activities. The Informed Consent specifies, in lay and culturally appropriate language, all expectations from the participant including duration of study, number of doses and visits, procedures at each visit, safety documentation (including subject diary), use of contraceptives, restrictions on intravaginal product or device use, sampling plan, potential risks, stipend for participation in study, and relevant research scope.

All study-related questions by the subject should be responded to before completion of the Informed Consent. The subject will be provided ample time to consider their potential participation, including time to consult with friends, family, and primary care provider if desired. The completed Informed Consent form will be verified for its proper completion. A signed copy of the Informed Consent will be provided to the subject and the original will be kept on file in the subject's study file.

#### 5.2 Inclusion/Exclusion Criteria

Participants will meet all the stated inclusion criteria and not possess any of the exclusion criteria to be eligible to participate in this study. Only subjects that are eligible based on the study inclusion and exclusion criteria will be enrolled in the study.

#### 5.3 Evaluation of Eligibility Criteria

The Investigator will evaluate whether a subject meets the study's inclusion/exclusion criteria at screening and enrollment and before administering any study product. The Investigator will be responsible for ensuring that the evaluation of eligibility criteria is addressed for all subjects enrolled in the study.

#### 5.4 Demographics

Demographics data will be collected from all study participants, including date of birth, race, and ethnicity.

#### 5.5 Clinical Evaluations

All clinical procedures summarized in this section will be performed according to the site's SOC SOPs.

#### 5.5.1 Medical History

A detailed medical/surgical/gynecologic/sexual history will be obtained. Changes in medical history, if applicable, will be reviewed at each visit.

A review of body systems will be performed by the Investigator to screen for exclusion criteria.

Subjects will be asked about current drug and alcohol use by the Investigator for evaluating eligibility.

### 5.5.2 Vital Signs

Vital signs, including blood pressure, heart rate, and body temperature, will be measured and recorded. Vital sign measurements will be obtained after the subject has been sitting quietly for at least 5 minutes. When taking an oral temperature, assure the subject has not had any recent hot or cold beverages or has recently smoked, including e-cigarettes. The Investigator should use clinical judgment when characterizing bradycardia among health subjects, eg, conditioned athletes.

#### 5.5.3 Gynecologic Examinations

A full gynecologic examination (speculum) will be performed **after** swab for vaginal pH is collected.

Targeted physical and/or gynecologic examination (speculum), will be performed at any subsequent or unscheduled visit if necessary due to an AE.

#### 5.5.4 Concomitant Medications

Concomitant medications that will be taken during the study, including all over-the-counter medications, vitamins, and nutritional supplements, will be recorded and should include at a minimum: start date, stop date or continuing, and indication/reason.

#### 5.5.5 Height and Weight

Body weight and height will be recorded.

#### 5.6 Laboratory Evaluations

Specimens collected for NAATs will be processed by the sites and shipped to a central laboratory for testing. All other laboratory testing and staining of used applicators will be performed onsite.

#### 5.6.1 Pregnancy Testing

Subjects of reproductive potential, including those with history of tubal ligation, will be required to provide a urine specimen to be tested for uHCG. This test will be performed at each site using the SOC testing materials and procedure.

Negative results must be obtained prior to dosing. Women who test positive for pregnancy will be excluded from participating in this study and be referred for follow-up as per clinic protocol (see Section 6.6.2 Pregnancy).

#### 5.6.2 Vaginal pH Testing

Swab for vaginal pH reading is collected prior to introduction of speculum for gynecologic exam. Specimen collection and vaginal pH testing procedures is detailed in the Manual of Procedures (MOP).

# 5.6.3 Nucleic Acid Amplification Tests for Chlamydia trachomatis/Neisseria gonorrhoeae

All women will have vaginal swabs collected all visits (screening, enrollment, and each intervention visit and follow-up visit) for NAATs. Swabs will be collected by clinician when speculum exams are performed; otherwise vaginal swabs will be self-collected by subject while in clinic. Specimens will be collected using the specific collection/transport kit materials and package insert instructions as designated by the central laboratory. Specimens will be shipped to the central laboratory according to procedure and as included in the MOP. All positive results will be reported to the study site for follow-up.

#### **5.6.4** Staining of Used Applicators

Sites will collect returned unused product and used applicators at each study visit. Site staff is responsible to visually inspect unused study product to confirm package seal is intact/not broken. If the seal is broken the applicator should be assessed for use (appears full of gel and unused). The used applicators will be tested onsite to validate vaginal insertion by using staining with trypan blue. Staff performing staining procedures will be trained and procedures will be detailed in the MOP.

#### 5.7 Subject eDiaries

Each subject will be provided with a secure validated eDiary software application downloaded to their personal cellular telephone or tablet to collect, at minimum, subject-reported sexual activity and study product use data. The eDiary application will be de-identified using the subject number assigned at the time of screening; research staff will receive, and review data identified only by the subject number throughout the course of the study.

The Investigator or designee will ensure each subject is trained in the importance of the eDiary and on its use. The instruction on maintaining the eDiary should include fields that must be completed and how the subject should record data within them. All eDiary entries will be reviewed on a regular basis, with subjects at each follow-up visit. Study sites must encourage eDiary recording by subjects via text messaging or direct contact with subjects. All eDiary entries will become part of the subjects' study record.

#### 5.8 Procedures by Visit

#### 5.8.1 Screening (Visit 0; Weeks -6-0)

Subjects who wish to participate in the study will be asked to sign and date the Informed Consent and HIPAA forms prior to any study-specific procedures. All subjects will be provided with a copy of their own signed and dated Informed Consent form. The Investigator must keep a subject screening log, subject enrollment log, and subject identification log for identifying all subjects having signed Informed Consent and HIPAA forms.

The following will be recorded by research staff in the source documents and CRF, as required:

- 1. Informed consent and HIPAA forms completed
- 2. Demographic data
- 3. Evaluation of inclusion and exclusion criteria
- 4. Medical/surgical/gynecologic/sexual history
- 5. Concomitant medication: all medications taken will be recorded in standard data collection forms with attention to drug route, daily dose, duration, start date, stop date, and indications
- 6. Self-collected vaginal swab for CT and GC NAATs

Subjects will be asked to return to the clinic after receipt of negative CT and GC NAAT results, preferably in 1 week  $\pm 7$  days for enrollment. Enrollment must be completed within 45 days of screening.

If NAAT results are positive, subjects must be treated according to SOC prior to enrollment. To meet eligibility criteria, these subjects will not be enrolled until 3 to 4 weeks after screening (at least 21 days after treatment).

#### 5.8.2 Rescreening

Subjects do not need to be rescreened if enrollment is within 45 days of initial screening. If more than 45 days, Informed Consent and Screening Visit assessments/procedures should be repeated.

#### 5.8.3 Enrollment/Visit 1 (Week $0 \pm 7$ days)

Subjects must be asked to abstain from vaginal intercourse in the 24 hours preceding Study Visit 1. The following will be recorded by research staff in the source documents and CRF:

- 1. Evaluation of inclusion and exclusion criteria
- 2. Evaluation of eligibility criteria
- 3. Demographic data
- 4. Completed Female Sexual Function Index (FSFI) and Sexual Function Questionnaire (SFQ)
- 5. Updated Medical/surgical/gynecologic/sexual history
- 6. Last menstrual period (date, if known)
- 7. Concomitant medication: all medications taken will be recorded in standard data collection forms with attention to drug route, daily dose, duration, start date, stop date and indications
- 8. Body height and weight
- 9. Vital sign measurements (blood pressure, heart rate, temperature)
- 10. Physical exam
- 11. Pregnancy test (urine)
- 12. Vaginal pH\*
- 13. Clinician-collected vaginal swab for CT and GC NAATs
- 14. Gynecologic examination\* (speculum, performed by clinician)
- 15. Randomization and issuance of study product (4-week supply based subject estimation of projected use)
- 16. Instructions on eDiary setup and use

Should subject be menstruating at time of scheduled visit, the visit may be rescheduled during the 7-day visit window, if possible.

Randomization, training, and verification of subject understanding, competency, and willingness to administer study product as directed is documented prior to issuance of study product.

If a subject's CT/GC NAAT results are positive at the enrollment visit, the subject should be immediately terminated from the study, IP accountability conducted, and all used/unused kits

\*Swab for vaginal pH reading is collected prior to introduction of speculum for gynecologic exam.

returned to the clinic. An Early Termination Visit should be performed to complete all procedures indicated for Visit 5 with the exception of repeat GC/CT NAAT testing. The subject should have SOC treatment for the infection and should be encouraged to return for a post-intervention follow-up visit approximately 4 weeks  $\pm 7$  days from Early Termination Visit or last

### 5.8.4 Visits 2 Through 4 (Weeks 4-12 $\pm$ 7 days)

Subjects must be asked to abstain from vaginal intercourse in the 24 hours preceding Study Visits 2 through 4. The following will be performed, and research staff will record results in the source documents and CRF:

- 1. Changes in the following since Screening Visit:
  - a. AEs

IP use.

- b. Concomitant medications
- 2. Pregnancy test (urine)
- 3. Self-collected vaginal swab for CT and GC NAATs
- 4. Targeted physical exam, if needed based on symptoms
- 5. Subject diary review (sexual activity, product use since last visit)
- 6. Return of all unused study product and used applicators
- 7. Issuance of additional study product (4-week supply based on prior month's usage or per subject estimation of projected use)

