| Subject Satisfaction with Product              |                      |   |                  |                  |                   | X                                  |  |
| Subject Sexual Satisfaction                    |                      |   |                  |                  |                   | X                                  |  |
| Female Sexual Function Index (FSFI)            |                      | X   |                  |                  |                   | X                                  |  |
| Sexual Function Questionnaire                  |                      | X   |                  |                  |                   | X                                  |  |

 Screening period may be up to 45 days. Subjects will be asked to return 7 days after Screening Visit. If subjects NAAT results are positive, they will be first treated by SOC then will return 3-4 weeks after Screening Visit (at least 21 days after treatment) for Enrollment/Visit 1. If the screening period extends past 45 days, subjects will not be enrolled and will need to be rescreened.

 Subjects must be asked to abstain from vaginal intercourse in the 24 hours preceding Study Visits 2 through 5.

Figure 1 **Schematic Flow of Study Design** 

 CT/GC NAAT testing is not required at this visit if subject was discontinued due to positive NAAT. For early termination, procedures for V5 should be followed with CT/GC NAAT testing required.

<sup>(4) Subjects will be asked to return  $\pm$  7 days within each visit window.

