#### 5.8.5 Visit 5 (Week $16 \pm 7$ days)

Subjects must be asked to abstain from vaginal intercourse in the 24 hours preceding Study Visit 5. The following will be performed, and research staff will record results in the source documents and CRF:

- 1. Changes in the following since last visit:
  - a. AEs
  - b. Concomitant medications
- 2. Pregnancy test (urine)
- 3. Self-collected vaginal swab for CT and GC NAATs
- 4. Targeted physical exam, as needed, based on symptoms
- 5. Subject diary review (sexual activity, product use since last visit)
- 6. Completed FSFI, SFQ, subject satisfaction with product, and subject sexual satisfaction questionnaires

7. Return of all unused study product and used applicators

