#### 6.2 Definitions

#### **Adverse Event (AE)**

Any untoward medical occurrence in a clinical investigation subject who has received a study product intervention and that does not necessarily have to have a causal relationship with the study product. An AE can, therefore, be any unfavorable and unintended sign (including an abnormal laboratory finding, for example), symptom, or disease temporally associated with the use of a study medicinal product, whether or not considered related to the study medicinal product.

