#### **Treatment-emergent Adverse Event (TEAE)**

A TEAE is any AE occurring after the application of the study product and within the time of residual product effect, or pre-existing medical condition that worsens in intensity after the application of study product and within the time of residual product effect. The time of residual product effect is 7 days after the dose of the study product, when the effect of the product is still considered to be present based on change of vaginal pH from baseline.

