### **6.3** Safety Reporting Requirements

#### **6.3.1** Reporting Interval

All AEs and SAEs will be collected and recorded following randomization.

The Investigators will follow all AEs that are deemed at least possibly related to investigational product and SAEs until resolution (return to pre-intervention status or stabilization of conditions deemed as chronic), even if this extends beyond the study-reporting period.

A subject will be considered as lost to follow-up if participation in AE assessment is not continued after:

- Three unsuccessful attempts at telephone contact (separated by at least 24 hours) following missed AE assessment visit or telephone consultation; followed by
- Issuance of a certified letter to last documented address of subject, and no response within 7 days of mailing

At any time after the completion of the study, if an Investigator becomes aware of an SAE that is suspected to be related to the investigational product, the Investigator will report the event to ICON GPHS within 24 hours of awareness. The Investigator will ensure that the appropriate IRB has been notified of the reported SAE in a timely manner per internal IRB reporting requirements.

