8.9.1 Adverse events

A summary of all adverse events that were reported will be presented by Medical Dictionary for Regulatory Activities® (MedDRA®-version 20.1 or higher) coding (System Organ Class and Preferred Term) by highest severity (one report by highest severity for each subject for that adverse event).

The incidence of adverse events (new or worsened) will be summarized by system organ class, preferred term, severity, and relationship to study intervention. The incidence of death, SAEs, and AEs leading to discontinuation will be summarized separately by system organ class and preferred term. Lastly, a summary of AEs by system organ class and relationship to study interventions will be provided.

An overall AE table will also be provided which provides a high-level of AE findings. As a part of this summary, subject & event counts for genitourinary events of FDA interest will be noted.

All adverse events will be listed.

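### Protocol 5.8.4 has sites ask about adverse events back to Screening at Visits 2 to 4, against the protocol's own start at randomization, and SAP 8.9.1 states no onset rule that would remove pre-gel events

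*Protocol*

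**What the plan says.** Protocol 5.8.4 covers Visits 2, 3 and 4. Its first item has staff record "Changes in the following since Screening Visit", with AEs and concomitant medications beneath it. The matching item for Visit 5 (Section 5.8.5) reads "Changes in the following since last visit", and Visit 6 (Section 5.8.6) uses the same words.

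Section 6.3.1 sets the reporting interval: "All AEs and SAEs will be collected and recorded following randomization". Section 6.2 defines an AE as "Any untoward medical occurrence in a clinical investigation subject who has received a study product intervention". It then defines a treatment-emergent event: "A TEAE is any AE occurring after the application of the study product and within the time of residual product effect". That definition also covers a pre-existing condition that worsens, and it sets the residual effect at 7 days after a dose. On the interval before enrollment, the first footnote to Table 1 says "Screening period may be up to 45 days".

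SAP 8.9.1 begins "A summary of all adverse events that were reported will be presented", with each subject contributing one report per event at the highest severity. It adds incidence tables of new or worsened AEs and an overall AE table in which "subject & event counts for genitourinary events of FDA interest will be noted". SAP 8.9 plans no statistical tests on safety data. In the SAP text available to me, the term TEAE appears only in the abbreviation list.

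**The concern.** A site cannot follow both 5.8.4 and 6.3.1. Under 5.8.4, a woman positive at Screening is asked about a period that includes her infection and its antibiotic treatment, all before any gel. Genitourinary symptoms are a plausible local effect of an acid gel, and Appendix A grades vaginal inflammation, pain, burning and pruritus as the anticipated AEs. An untreated infection can produce similar complaints.

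Events from before randomization should be similar in the two arms. If they were tabulated as AEs they would raise both proportions and make the gels look more alike than they are. Descriptive AE rates are the only safety comparison planned, so what counts as an AE should be settled before unblinding. The same early window is also opened at three successive visits, so one early event could be entered more than once.

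**Working it through.** The documents give no AE rate or safety precision, so there is no planned figure to reproduce. The check compares the texts, counts days, and then gives an illustration with assumed rates.

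**1. Where the AE window starts**

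| Place | Start |
|---|---|
| Protocol 5.8.4 (Visits 2 to 4) | Screening Visit |
| Protocol 5.8.5 and 5.8.6 (Visits 5 and 6) | previous visit |
| Protocol 6.3.1 | randomization |
| Protocol 6.2, AE | receipt of study product |
| Protocol 6.2, TEAE | application of product, up to 7 days after a dose |
| Protocol Table 1 | AE assessment from Visit 1, none at Screening |
| SAP 8.9.1 | none stated |

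Section 5.8.4 is the outlier. The back-reference does suit concomitant medications, which Table 1 collects from Screening onward. It does not suit AEs.

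**2. How far back the window reaches**

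Let d be the days from Screening to randomization and v the days from randomization to the visit (28, 56 or 84). The window is d + v days, and the share before randomization is d/(d + v). I take d = 7 for a woman negative at Screening (Table 1 footnote), d = 28 for one positive at Screening (upper end of 3 to 4 weeks), and d = 45 as the maximum.

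| d | Visit 2 | Visit 3 | Visit 4 |
|---|---|---|---|
| 7 | 7/35 = 20% | 7/63 = 11% | 7/91 = 8% |
| 28 | 28/56 = 50% | 28/84 = 33% | 28/112 = 25% |
| 45 | 45/73 = 62% | 45/101 = 45% | 45/129 = 35% |

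These are shares of calendar days, not of events. The 21-day antibiotic washout does not close the gap. A woman positive at Screening is treated after Screening and enrolled at least 21 days after treatment (Section 5.8.1), so her treatment falls inside the window.

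**3. Whether a later step removes such events**

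- Protocol 8.4.2 and SAP 8.9.1 do not restrict the tables to TEAEs.
- Restricting incidence to new or worsened AEs names no reference date, so it does not by itself exclude onset before the gel.
- The Safety population (SAP 6.3) selects women who applied product. It does not select events by onset.
- Even with 6.3.1 followed exactly, an event between randomization and first gel use is not treatment-emergent under 6.2, yet no stated rule keeps it out of the tables.

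**4. Direction and size if such events are tabulated**

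Suppose a fraction b of women in each arm has a recorded pre-gel local event, independent of later events. A true incidence x is then reported as 1 − (1 − x)(1 − b). All rates here are assumed; x is 10% on AMPHORA and 5% on placebo.

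| b | AMPHORA | Placebo | Difference (points) | Ratio |
|---|---|---|---|---|
| 0 | 10.0% | 5.0% | 5.0 | 2.00 |
| 2% | 11.8% | 6.9% | 4.9 | 1.71 |
| 5% | 14.5% | 9.75% | 4.75 | 1.49 |
| 10% | 19.0% | 14.5% | 4.5 | 1.31 |

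For example, at b = 5%: 1 − 0.90 × 0.95 = 14.5% and 1 − 0.95 × 0.95 = 9.75%. With 20% against 10%, the ratios for the same b are 1.83, 1.66 and 1.47, and the differences 9.8, 9.5 and 9.0 points. The ratio moves noticeably and the difference little. Nothing in the documents fixes b, and b is zero if sites follow 6.3.1.

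**5. Repeated asking**

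The main AE table takes one report per subject per event, so a duplicate cannot change it. The overall table counts genitourinary events as well as subjects, so an unreconciled duplicate could raise that event count.

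**The case against.** The strongest reply is that the protocol already answers the question. Section 6.3.1 is the dedicated rule on the reporting interval, Section 6.2 ties an AE to receipt of product, and Table 1 has no AE assessment at Screening. Medical history is updated at Visit 1, so earlier conditions have a place outside the AE record. Exclusion 12 removes women with signs of persistent infection. On this view 5.8.4 is one loose checklist line, shared with concomitant medications.

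Much of this stands. A reader might infer that index-infection and antibiotic events do enter the safety tables and do dilute the comparison. The documents do not support that: it happens only where a site lets 5.8.4 override 6.3.1 and 6.2. A reader might also infer that asking three times inflates AE incidence; the one-report rule prevents that. The exposed group is limited too, since women negative at Screening return after about a week. Any contamination would be balanced in expectation, and no safety test is planned that could lose power.

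The reply does not remove the conflict. Section 6.3.1 can be read as saying when recording takes place rather than which onset dates qualify, and Visit 2 is after randomization. The procedure list for Visit 1 (Section 5.8.3) contains no AE item, although Table 1 marks one, so in the visit lists the first AE question is the one worded back to Screening. Balance between arms is no defence for a ratio, because equal additions are what move it towards 1.

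One further limit: SAP Section 1 places the table templates in a separate document, and the text available to me does not include SAP 7.2. Either could hold a date rule that I have not seen.

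**Conclusion.** Wrong as written, and minor. The AE window in Protocol 5.8.4 contradicts 6.3.1, 6.2, 5.8.5 and 5.8.6, and can reach 45 days before randomization. SAP 8.9.1 states no onset rule that would remove an event recorded under that wording, although the protocol already has a TEAE definition that would.

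Pre-gel events can therefore enter the AE tables in both arms. If they do, the effect is to pull the descriptive ratio of local AEs towards 1, with little change in the risk difference. This assumes that some sites apply 5.8.4 literally and that pre-gel events are equally common in the two arms. The size is unknown, and the ratios above only illustrate direction. Repeated asking bears on event counts alone, chiefly the genitourinary line. Neither the primary nor the secondary efficacy analysis is affected.

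**What to change.** In Protocol 5.8.4, item 1, change the AE window to *since last visit (at Visit 2: since randomization)*. The reference to Screening can stay for concomitant medications if wanted. If an amendment is not practical, a memo to sites would serve.

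In SAP 8.9.1, before unblinding:

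- base the AE summary tables on TEAEs as defined in Protocol 6.2, using AE start dates;
- list the remaining AEs separately, including those before first use and those beyond the 7-day residual period;
- count a continuing event once.

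Using the existing definition matters: a new rule based only on first use would add a second cut-off that differs from 6.2.

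The cost is one phrase in the protocol and a short addition to the SAP. No new data should be needed. Product use is recorded in the eDiary (Section 5.7), and I assume that the AE form captures a start date, since the documents do not list its fields.
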